3.2. Randomization and Blinding

Subjects who are candidates for enrollment into the study will be assigned a sequential and unique subject number by the Investigator after the subject has provided written informed consent. Once a subject number has been assigned, it cannot be reused.

Subjects who have provided written informed consent will be evaluated for eligibility by the Investigator to ensure that the entry criteria (see Protocol Sections 8.2 and 8.3) have been satisfied and that the subjects is eligible for participation in this clinical study.

Two TVB-2640 dose levels are planned to be evaluated in a sequential fashion: 25 mg and, if study suspension criteria are not met at the 25 mg dose level (see Protocol Section 7.2), 50 mg. At each dose level, subjects will be randomly assigned to TVB-2640 or placebo at a 2:1 ratio, with randomization stratified by type 2 diabetes mellitus (DM) status. The 50 mg dose level will also be stratified by country:

- 25 mg dose level: TVB-2640 (Planned N=30) and Placebo (Planned N=15)
- 50 mg dose level: US: TVB-2640 (Planned N=30) and Placebo (Planned N=15); China: TVB-2640 (Planned N=18) and Placebo (Planned N=9); Total: TVB-2640 (Planned N=48) and Placebo (Planned N=24)

Randomization will be done via Interactive Web Response System (IWRS). Subjects are to receive their first study drug dose on Day 1 within 24 hours after randomization.

At both dose levels, subjects will receive TVB-2640 or placebo QD PO for 12 weeks.

Study drug will be dispensed to subjects in a single-blinded fashion. All other study personnel, with the exception of personnel conducting/interpreting imaging studies (see Protocol Section 11.1) at each study center, will be unblinded to the subject's treatment assignment.

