3.3. Sample Size Considerations

The sample size is based on a fixed-sequence strategy which tests for a treatment difference in the primary endpoint (percent change at Week 12 in liver fat from baseline as determined by

MRI-PDFF) between each TVB-2640 dose group versus placebo. The fixed-sequence strategy will start with the highest dose group comparison. If statistically significant, then testing will proceed to the low dose group comparison. Each TVB-2640 dose group will be compared to the pooled placebo group using an F-test test from an analysis of covariance (ANCOVA) model with fixed effects for the stratification factor (diabetes presence/absence) and treatment group (i.e., TVB-2640 dose groups and pooled placebo) and with the baseline MRI-PDFF value as a covariate. Since the primary efficacy endpoint may not be normally distributed, the non-parametric Wilcoxon rank-sum test is conservatively used, instead of the F-test, for power calculations.

The sample size is based on a conservative assumption that the primary analysis is going to be performed in the US population only, resulting in 30 evaluable subjects in the placebo group, and 30 evaluable subjects in each of the TVB-2640 dose levels. Based on Patel (2016), it is conservatively assumed that the primary endpoint has a standard deviation of 30. Power calculations assume the primary endpoint is lognormally distributed with a standard deviation of 30, there are at least 30 evaluable subjects in each treatment group, and the two-sided Wilcoxon rank sum test will be used to test each pairwise treatment difference at the 0.05 Type I error level. Under the fixed-sequence strategy which maintains an overall 0.05 Type I error rate, the study has at least 80% overall power to detect both treatment differences (i.e., both high dose versus placebo and low dose versus placebo), if each mean treatment difference is at least 24. If the study does not proceed to the high-dose level, (i.e., there are 30 evaluable subjects treated with 25 mg TVB-2640 and only 15 with placebo), then the study has at least 77% power to detect a mean treatment difference of at least 24. The study will have more power if the subjects from China are included in the primary analysis and the same assumptions of treatment difference and variability hold.

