3.5. Timing of Analyses

An interim analysis for SRC review will be performed after all of the subjects in the 25 mg dose level complete the 12-week treatment period. Details on data requirements and outputs required will be maintained in the SRC Plan or other related documents.

An additional SRC analysis was performed during the COVID pandemic to confirm safety prior to allowing the option for extended 50 mg cohort dosing.

The primary analysis of efficacy will be performed when all subjects in the US 50 mg cohort finish their final visit. The primary analysis will not include any data from China, due to delays and uncertainty of enrollment in the Chinese cohort.

An End of Study final analysis will be performed when the final subject completes the study and will include cumulative data from the US and China as applicable.

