7.3. Multiple Comparisons and Multiplicity

In order to control for multiple comparisons, the primary and key secondary efficacy analyses will be tested using a fixed-sequence strategy to maintain the overall Type I error rate at 0.05. Each test in the fixed-sequence, uses a 2-sided test at the 0.05 level of significance and starts with the primary efficacy analyses. The first comparison to be assessed for significance is the primary efficacy endpoint analysis of the high-dose group (50 mg TVB-2640) compared to placebo and if statistically significant, testing will proceed to the low-dose group (25 mg TVB-2640) comparison. If both comparisons of the primary efficacy endpoint are significant, then testing will proceed to the key secondary efficacy endpoint. The key secondary efficacy analyses will be tested in a similar fashion, first comparing the high dose group (50 mg TVB-2640) with placebo and if statistically significant, testing will proceed to the low dose group (25 mg TVB-2640) comparison.

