8.3.1.2. Additional Analyses of the Primary Efficacy Endpoint

The primary efficacy analysis will be repeated using the ITT population, ATP, and PP population. Analyses will be conducted with LOCF from Week 8 onward and repeated excluding missing data (no LOCF).

In addition to the primary analysis of Week 12 that includes all subjects who had no more than 12 weeks of study treatment, an analysis of the End of Treatment MRI-PDFF data including data from the extended dosing subjects will be performed in the mITT, ITT, ATP, and PP populations.

An analysis of MRI-PDFF data in the log scale will be performed in the mITT population. The log ratio of Week 12 to baseline [$\log(\text{Week 12}/\text{Baseline})$] will be analyzed using a similar

ANCOVA mode. In the event that model assumptions are not met for the primary efficacy analysis noted above, the analysis in the log scale will become primary.

At the time of the final analysis, the above analyses will be repeated using all data from the US and China. Subset analyses will be performed on the primary efficacy endpoints for subjects enrolled in US and China to evaluate the consistency of results between subjects enrolled in each country. The ANCOVA model will incorporate fixed effects for the stratification factor (diabetes presence/absence), country (US/China), treatment group (TVB-2640 50 mg and pooled placebo), and country-by-treatment interaction and with the baseline MRI-PDFF value as a covariate including all subjects in the mITT from US and China who received 50 mg or placebo.

A test for country-by-treatment interaction will be performed. If there is no interaction detected ($p \geq 0.05$), the primary efficacy endpoint, percent change from baseline in hepatic fat fraction at Week 12, as determined by MRI PDFF, will be analyzed using an ANCOVA model with fixed effects for the stratification factor (diabetes presence/absence) and treatment group (i.e., TVB-2640 dose groups and pooled placebo) and with the baseline MRI-PDFF value as a covariate including all subjects from US and China (with no fixed effect for country). If the country-by-treatment interaction is significant ($p < 0.05$) then a separate analysis will be performed on subjects enrolled in China in the 50 mg cohort. This analysis is not powered to detect a significant difference but would be supportive/descriptive in nature to evaluate trends.

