8.3.2. Secondary Efficacy Endpoints and Analyses

MRI-PDFF Endpoints

Week 12 data for the secondary efficacy endpoints will be handled similarly to the handling used for the primary efficacy endpoint. That is, analyses will be performed both excluding data from subjects who required extended dosing beyond 12 weeks and including data from the extended dosing subjects as supplemental analyses.

The key secondary efficacy endpoint is the percentage of subjects with at least a 30% reduction in liver fat at Week 12, as determined by MRI-PDFF. Note that due to data collection precision, subjects with a reduction of at least 29.5% from baseline will count as responders. Differences between each TVB-2640 dose group (25 mg, 50 mg) and pooled placebo for the key secondary efficacy endpoint will be analyzed using CMH methods. The key secondary efficacy analyses will be based on a CMH test in the mITT population to compare each TVB-2640 dose group with placebo, adjusting for the stratification factor (diabetes presence/absence). For the final end

Sponsor: Sagimet Biosciences
Protocol Number: 3V2640-CLIN-005
Version and Date: Final Version 1, 02June2020

of study analysis, if a country-by-treatment interaction is found in the primary efficacy endpoint, the subjects from the US and China in the 50 mg cohort will be analyzed separately for the key secondary efficacy endpoint.

To check for other possible interactions, i.e., diabetes strata-dependent treatment effects, the Breslow-Day test will be performed; if the p-value of the Breslow-Day test is ≥ 0.05 , the treatment-by-strata interaction is deemed not significant. However, if the interaction effect is statistically significant (i.e., p value < 0.05), then the Gail and Simon test will be used to test for the qualitative interaction at a significance level of 0.05 and provided as an aid for interpretation of the CMH results. The estimated response rates and the corresponding exact 95% confidence interval based on a binomial distribution will be calculated for each treatment group. The exact 95% confidence limit for the CMH estimate of the common risk difference will also be obtained; a Wald asymptotic approximation with continuity correction is an acceptable substitute for the exact limits in the event of computational difficulties.

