9. CHANGES TO THE PLANNED ANALYSES

The timing of the primary efficacy analysis will be based on completion of the US 50 mg cohort. The protocol indicated the initial analysis of the primary efficacy endpoint would be performed using subjects from US and China and include country as an effect in the ANCOVA model. Given the delays in enrollment in China due to COVID-19, the primary analysis has been adjusted to only include the US cohorts and a modified ANCOVA model as described above.

The treatment group used for the presentation of data based on the mITT population has been modified from the protocol. Per the study protocol, the data were to be analyzed based on randomized treatment.

As a point of clarification and as noted for the key secondary efficacy analysis above, due to data collection precision, subjects with a reduction of at least 29.5% from baseline will count as responders. Similar conventions were used for the sensitivity analyses of that endpoint using different responder definitions.

Since one subject received the incorrect study treatment (active instead of placebo), an as-treated population (ATP) has been added to the SAP. The ATP will be used to evaluate the treatment differences in efficacy endpoints using treatment received instead of randomized treatment.

Due to the impact of COVID-19, all efficacy endpoints will be analyzed at End of Treatment and End of Study. The definition of those timepoints are described in section 3.1. Per the protocol, endpoints were evaluated at Week 12 and Week 16 but the differences in duration of treatment require further evaluation given the visits may not correspond to the number of weeks specified in the protocol visit schedule.

An additional SRC analysis was performed during the COVID-19 pandemic to confirm safety prior to allowing the option of extended 50mg cohort dosing. If additional SRC reviews are performed, they will be discussed in the CSR.

Additional supplementary and sensitivity analyses related to the protocol-planned analyses have been added to the SAP. Specifically, the absolute change from baseline in MRI-PDFF has been added in addition to the planned percent change. The change from Week 12 to Week 16 in MRI-PDFF has been added. ALT and AST normalization has been added as an additional analysis of the liver aminotransferases.

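### The supportive end-of-study US+China ANCOVA drops country after a test that checks only the interaction, although China's share differs across the three compared groups

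*SAP*

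**What the plan says.** The SAP makes the primary analysis US-only. Section 3.5: "The primary analysis will not include any data from China, due to delays and uncertainty of enrollment in the Chinese cohort". Section 9 declares this as a change from the protocol: "the primary analysis has been adjusted to only include the US cohorts". A later end-of-study analysis "will include cumulative data from the US and China as applicable".

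Section 8.3.1.2, on additional analyses, sets out the combined analysis in two steps.

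- **Step 1.** An ANCOVA in 50 mg and placebo subjects, with diabetes, country, treatment, country-by-treatment and baseline MRI-PDFF.
- **Step 2.** If the interaction p-value is at least 0.05, an ANCOVA of both doses and pooled placebo with diabetes, treatment and baseline, "including all subjects from US and China (with no fixed effect for country"). If it is below 0.05, Chinese subjects in the 50 mg cohort are analysed separately.

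Country is a randomization factor in one cohort only. Section 3.2: "The 50 mg dose level will also be stratified by country". Section 7.1 repeats this for the final analysis and says that selected models and tests follow the randomization strata. The 25 mg cohort has no China stratum.

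For the 30% responder endpoint, section 8.3.2 uses a CMH test "to compare each TVB-2640 dose group with placebo, adjusting for the stratification factor (diabetes presence/absence").

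**The concern.** An interaction test asks whether the drug effect differs between countries. It does not ask whether liver-fat change differs between countries under the same treatment. A non-significant interaction therefore gives no ground for removing the country main effect.

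This would matter little if country were balanced across the compared groups. Within the 50 mg cohort it is balanced: China is 18/48 of active and 9/24 of placebo, both 37.5%. Pooling that placebo with the placebo of the all-US 25 mg cohort breaks the balance, and randomization does not protect the pooled contrasts against a country difference. The pooled 25 mg comparison sets an all-US group against a placebo group that is 23% Chinese.

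At stake is whether the combined estimates, reported beside the US ones, are distorted in a direction that nobody can know in advance.

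**Working it through.** **Inputs.** Planned numbers by group and country from SAP 3.2. From SAP 3.3: two-sided 0.05, a design difference of 24 points, and the SD ("it is conservatively assumed that the primary endpoint has a standard deviation of 30"). D is the China-minus-US difference in percent change under the same treatment, after adjustment for baseline and diabetes. It is not in the documents, so a range is assumed. A negative contrast favours the drug.

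**The plan's own figures.**
- Total: 30 + (15+15+9) + (30+18) = 117, as stated.
- Power: 30 v 30 with difference 24 and SD 30 gives 87.3% per pair and 79.2% for both (normal formula, correlation 0.5 from the shared placebo). A Wilcoxon test on lognormal data with an assumed placebo mean of 100 to 108 gives 83-84% for both. This is consistent with the stated figure of at least 80%.

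**China shares.** 25 mg 0/30 = 0; pooled placebo 9/39 = 0.231; 50 mg 18/48 = 0.375.

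**Bias without a country term** = (share in dose group - share in placebo) x D.
- 25 mg: (0 - 0.231)D = -0.231D
- 50 mg: (0.375 - 0.231)D = +0.144D

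At D=10 the biases are -2.3 and +1.4 points. At D=20 they are -4.6 and +2.9.

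**Standard errors.** Without country:
- 25 mg: 30 x sqrt(1/30 + 1/39) = 7.29
- 50 mg: 30 x sqrt(1/48 + 1/39) = 6.47

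With country, the within-group country sum of squares is W = 39(0.231)(0.769) + 48(0.375)(0.625) = 6.92 + 11.25 = 18.17. Then:
- 25 mg: 30 x sqrt(1/30 + 1/39 + 0.231^2/18.17) = 7.46
- 50 mg: 30 x sqrt(1/48 + 1/39 + 0.144^2/18.17) = 6.55

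**Two-sided type I error** (simulated ANCOVA at planned N, SD 30):

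| \|D\| | 25 mg, no country | 50 mg, no country | Both, with country |
|---|---|---|---|
| 5 | 5.2% | 5.1% | 5% |
| 10 | 5.9% | 5.4% | 5% |
| 20 | about 8% | 6.3% | 5% |

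Hand check for 25 mg at D=20. The shift is 4.62/7.29 = 0.63 SE. Omitting country inflates the residual SD by sqrt(1 + 400 x 18.17/(900 x 112)) = 1.035, so the critical value of 1.98 becomes about 2.05. The rejection probability is about Phi(-1.42) + Phi(-2.68) = 0.078 + 0.004 = 8.2%.

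**Does the interaction test screen this out?** No. It gives p>=0.05 about 95% of the time whatever the main effect. Restricting to those runs changes the error rates by no more than 0.1 point.

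**Direction for 25 mg.** The sign of D decides the kind of harm.
- *Positive D* makes 25 mg look better than it is. The fixed sequence says that, for 50 mg, "if statistically significant, testing will proceed to the low-dose group (25 mg TVB-2640) comparison". If 50 mg works (24 points) and 25 mg does nothing, the chance of a favourable 25 mg result within that sequence is about 2.5% at D=0, 4.6% at D=10 and 7.8% at D=20. Repeat runs differ by about 0.2 point.
- *Negative D* hides a working 25 mg dose. With a true 24-point effect on both doses, 25 mg power is 90% at D=0, 83% at D=-10 and 73% at D=-20, against 89% at any D with country. A false favourable 25 mg result becomes rarer, about 0.4% at D=-20.

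The 50 mg contrast is biased the opposite way and by less.

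**Sensitivity.** With about half the Chinese subjects (9 active, 5 placebo), the biases are -0.143D and +0.088D, and D=20 gives 6.0%/5.1%. At an assumed SD of 20, D=10 gives 7.0%/5.8%.

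**Responder endpoint.** Assume no drug effect, a US response of 16.7%, a Chinese response of 30% or 40%, and diabetes split 50/50 and unrelated to response. The pooled CMH error is then 5.8% or 7.8% for 25 mg and 5.0% or 5.7% for 50 mg.

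**The case against.** The strongest reply is that nothing confirmatory depends on this model. SAP 3.5, 8.3.1.1 and 9 all make the primary analysis US-only. Estimates free of this bias are already planned: the US-only contrast for 25 mg, whose subjects are all in the US, and for 50 mg the interaction model, which contains country. Section 7.2 adds analyses by country. D is assumed, must survive adjustment for baseline fat and diabetes, and at 20 points would be 20/24 = 83% of the whole design effect. Chinese enrolment was itself uncertain. All of this stands, and it limits the point to a minor one. It does not defend the model: the pooled estimate is still biased whenever D is not zero, and the term that removes the bias is already in the preceding model.

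Stronger readings are tempting but not supported.

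- **That the trial's overall error rate is at risk.** A reader might infer this because SAP 8.3.1.1 ties the fixed sequence to the final analysis, and protocol 13.2.2 still words the pooled model without country as primary. But protocol 13.2.2 leaves US/China data handling to the SAP, and SAP 9 openly changes the plan. The SAP 8.3.1.1 phrase is an ambiguity of wording, not evidence that the combined analysis is confirmatory.
- **That the choice of minimum effective dose is distorted**, because the gap between doses shifts by 0.231D + 0.144D = 0.375D. No 50-versus-25 mg test is planned. Protocol 13.2.2 seeks that dose through dose-versus-placebo tests, which the SAP's primary analysis runs in US subjects.
- **That false 25 mg claims rise for either sign of D.** Two-sided rejections do rise, but for negative D almost all of them go against 25 mg.

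**Conclusion.** The point holds as a minor improvement to a supportive analysis. A non-significant interaction does not justify dropping country, and the unequal China shares follow directly from the planned numbers. The resulting bias is -0.231D for 25 mg and +0.144D for 50 mg. It is zero if D is zero, negligible in its effect on error rates at |D|=5, modest at 10, and noticeable only for a country difference near the size of the design effect.

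The error rates rest on planned rather than mITT numbers, SD 30, a common treatment effect across countries and an assumed D. The US-only primary analysis, the by-country analyses and the 50 mg/placebo interaction model are not affected.

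**What to change.** In SAP 8.3.1.2, p>=0.05 branch only, replace the parenthesis that excludes country with a fixed effect for country (US/China). This agrees with SAP 7.1. Leave the p<0.05 branch as written; extending a common-effect model to that branch would be a separate change that this point does not support.

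Cost: one phrase in the SAP. The SE goes from 7.29 to 7.46 for 25 mg (power at 24 points 90.4% to 89.0%) and from 6.47 to 6.55 for 50 mg (95.7% to 95.3%). With 9+5 Chinese subjects the SEs go from 7.46 to 7.57 and from 6.99 to 7.03.

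Optional, in SAP 8.3.2: stratify the pooled 50 mg CMH test by diabetes and country. At response rates of 53.4% versus 16.7% its power goes from 96% to 95.5%. For 25 mg, report the responder comparison from the US-only analysis already planned. Stratifying the pooled 25 mg test by country would leave only US subjects informative, so it would repeat that analysis, with power of 87% against 92% for the unstratified pooled test.

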8.3.2. Secondary Efficacy Endpoints and Analyses

MRI-PDFF Endpoints

Week 12 data for the secondary efficacy endpoints will be handled similarly to the handling used for the primary efficacy endpoint. That is, analyses will be performed both excluding data from subjects who required extended dosing beyond 12 weeks and including data from the extended dosing subjects as supplemental analyses.

The key secondary efficacy endpoint is the percentage of subjects with at least a 30% reduction in liver fat at Week 12, as determined by MRI-PDFF. Note that due to data collection precision, subjects with a reduction of at least 29.5% from baseline will count as responders. Differences between each TVB-2640 dose group (25 mg, 50 mg) and pooled placebo for the key secondary efficacy endpoint will be analyzed using CMH methods. The key secondary efficacy analyses will be based on a CMH test in the mITT population to compare each TVB-2640 dose group with placebo, adjusting for the stratification factor (diabetes presence/absence). For the final end

Sponsor: Sagimet Biosciences
Protocol Number: 3V2640-CLIN-005
Version and Date: Final Version 1, 02June2020

of study analysis, if a country-by-treatment interaction is found in the primary efficacy endpoint, the subjects from the US and China in the 50 mg cohort will be analyzed separately for the key secondary efficacy endpoint.

To check for other possible interactions, i.e., diabetes strata-dependent treatment effects, the Breslow-Day test will be performed; if the p-value of the Breslow-Day test is ≥ 0.05 , the treatment-by-strata interaction is deemed not significant. However, if the interaction effect is statistically significant (i.e., p value < 0.05), then the Gail and Simon test will be used to test for the qualitative interaction at a significance level of 0.05 and provided as an aid for interpretation of the CMH results. The estimated response rates and the corresponding exact 95% confidence interval based on a binomial distribution will be calculated for each treatment group. The exact 95% confidence limit for the CMH estimate of the common risk difference will also be obtained; a Wald asymptotic approximation with continuity correction is an acceptable substitute for the exact limits in the event of computational difficulties.

Similar responder analyses will be performed using response level definitions of 20%, 40%, and 50%. As done for the key secondary endpoint efficacy endpoint, subjects with a reduction of at least 19.5%, 39.5%, and 49.5% from baseline, respectively, will count as responders. Analyses will be repeated in the ITT, ATP, and PP populations. Analyses of the key secondary endpoint performed in the ATP populations will include summaries of all subjects in the analysis population, as well as the subset of subjects that have at least 8 weeks of treatment and an evaluable assessment on/after 8 weeks (i.e., the same subjects in the mITT population).

Similar responder analyses will be performed using reduction in liver fat at End of Study in the mITT, ITT, and ATP populations.

A scatter plot of End of Treatment body weight changes versus End of Treatment liver fat changes will be graphed by treatment and overall in the ATP. A subset will also be run in subjects with at least a 30% reduction in liver fat at Week 12.

In the key secondary analysis, missing Week 12 values for MRI-PDFF will be imputed with the last post-baseline observation on or after Week 8 in the mITT population. Sensitivity analyses excluding subjects with missing data will also be performed.

Other Efficacy Endpoints

Other efficacy endpoints will be summarized using the ATP. A limited set of endpoints will be repeated in the ITT.

Liver aminotransferases will be evaluated using observed values and changes from baseline by study visit. Summaries will be performed for ALT and AST and will be presented by treatment group.

The changes at 12 weeks will be summarized for each treatment group and compared between each TVB-2640 dose group and pooled placebo using a linear mixed-effects model for repeated measures (MMRM). The model will include the stratification factor (diabetes presence/absence),

Sponsor: Sagimet Biosciences

Protocol Number: 3V2640-CLIN-005

Version and Date: Final Version 1, 02June2020

treatment group, visit, and treatment-by-visit interaction as the fixed effects, and baseline value as a covariate, and the model will use an unstructured variance-covariance matrix. The point estimates for the least-squares mean of the pairwise difference for each TVB-2640 dose group and pooled placebo comparison at each visit and the corresponding 95% confidence interval and two-sided p-value will be summarized. If convergence problems arise when fitting the model, a spatial power covariance structure will be used as a first step. If the model still has convergence issues, compound symmetry covariance structure will be employed.

For the end of study final analysis, if a country-by-treatment interaction is found in the primary efficacy endpoint, the subjects from the US and China in the 50 mg cohort will be analyzed separately. However, if no country-by-treatment interaction is found in the primary efficacy endpoint, the interaction may be explored within the secondary endpoints in a similar manner in order to determine if there is a significant interaction for any of the other endpoints (e.g., ALT or AST).

The model produces asymptotically consistent estimates when data are missing at random. No imputation of missing data will be required for these analyses. By definition, subjects without a baseline and at least 1 post-baseline value will be excluded from the MMRM analyses. Model assumptions (normality of residuals and parallel slopes) may be assessed. If assumptions are not met, then transformations will be done analogous to the primary efficacy analyses described above.

Similar analyses will be performed for:

- Lipid and lipoprotein parameters including low-density lipoprotein cholesterol (LDL-C), non-LDL-C, high-density lipoprotein cholesterol (HDL-C), non-HDL-C, total cholesterol, TG, apolipoprotein B (ApoB), and lipoprotein(a) (Lp[a]) particles, total Cholesterol:HDL ratio, LDL:HDL ratio (Note that the cholesterol and LDL to HDL ratios will be derived and do not come directly from the laboratory)
- NASH and fibrosis biomarkers including cytokeratin-18 (CK-18), fibrosis-4 (FIB-4), and enhanced liver function (ELF) or FIBROspect 2 or ProC3 test.
- Eicosanoids including 5-LOX-derived leukotriene B4 (LTB4), COX-derived prostaglandin E2 (PGE2), and 15-LOX-derived 15-hydroxyeicosatetraenoic acid (15-HETE) and lipoxin A4 (LXA4). For eicosanoids, descriptive statistics will be presented without any statistical testing.

The number and percentage of subjects with normalized ALT will be summarized by study visit and treatment group. Differences between each TVB-2640 dose group (25 mg, 50 mg) and pooled placebo for ALT normalization will be analyzed using CMH methods. The analyses will be based on a CMH test to compare each TVB-2640 dose group with placebo, adjusting for the stratification factor (diabetes presence/absence). Only subjects with ALT>ULN at baseline will be included in the ALT normalization analyses.

Similar analyses will be performed for AST.

A scatter plot of End of Treatment TG changes versus End of Treatment liver fat changes will be graphed by treatment and overall in the ATP. A subset will also be run in subjects with at least a 30% reduction in liver fat at Week 12

Sponsor: Sagimet Biosciences
Protocol Number: 3V2640-CLIN-005
Version and Date: Final Version 1, 02June2020

Subset analyses will be performed on relevant secondary efficacy endpoints for subjects enrolled in the US and China to evaluate the consistency of results between subjects enrolled in each country. The specific analyses performed by region will depend on the data that are ultimately collected in China. In the event that some efficacy parameters are not able to be evaluated in China, those analyses will not be performed.

